## 7.0 ADVERSE EVENTS

### 7.1 Definitions of adverse events

**Adverse Event (AE)** – Any untoward medical occurrence in a subject to whom a medicinal device has been administered, including occurrences which are not necessarily caused by or related to that product.

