### 7.3 Recording and reporting of Adverse Events

We do not anticipate that the use of the CE-marked TENS device will result in any serious adverse events. Participants will be given prior information regarding the reporting of adverse events and measure to take including instructions to contact the research team via a dedicated phone line.

Participants will be specifically queried regarding the following adverse events of special interest: any case of itching, skin breakdown, mild electrical burn, other skin allergies, or mild autonomic responses at each study visit, and reported related adverse events will be documented in an applicable adverse event form.

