### **8.5 Safety analysis**

The safety data (adverse events)- both numbers of subjects and events – will be summarised by randomised group and overall using descriptive statistics. No formal statistical tests comparing the randomised groups will be pre-specified.

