Trial design:

We will conduct a 2 x 2 parallel group (TENS versus placebo TENS x SEDRIC versus no additional education) feasibility RCT to compare use of TENS against placebo TENS with and without a patient-centred education programme. Permuted block randomisation will be implemented to allocate patients to trial arms. The intervention will last for 6 weeks, and patients recruited within the first eight months will be further followed up for 3 months. Outcomes assessments will be implemented at baseline, after six weeks treatment and at 3 months follow up. We will collect information regarding the recruitment rate, intervention uptake, outcome measure completion rate, attrition rate, blinding fidelity, efficacy related to the primary, secondary and other PROMs, and patients experience of intervention including acceptability and ease of intervention.

Randomisation:

A central randomisation facility (interactive voice response system, IVRS) will allocate the randomised therapy per patient. The IVRS, based at the Data Centre, will be available by telephone. Stratified permuted block randomization procedures will be utilised to allocate patients to groups (Patients allocation will be stratified by gender and age, ABPI values). Permuted block design (PBD) will be used to allocated patients to the PE+TENS, PE+Placebo TENS, TENS, Placebo TENS using 4-way randomisation throughout the whole time until the recruitment of a minimum of 20 subjects in the each of the larger comparison groups are achieved.

Sample size:

Details regarding sample size calculation can be found in section 8.7 of the full study protocol (version 2.0). Summarily, 16 participants per group will allow detection of an effect size of 1.0sd of ACD in active TENS group compared to placebo control. Allowing for 20% attrition, we will recruit 20 participants in each group, and therefore aim to recruit 80 patients.

Framework

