Differences in the changes in activPAL outcomes, ICD, SF-36 and ICQ scores, MPQ score, IPQ, GDS-SF, PSEQ, ABI, and Biomarkers will also be analysed and effect scores calculated using Chi-squared tests, Mann-Whitney U or Wilcoxon signed-rank tests as applicable for between and within-group comparisons and log-rank method for pooled samples.

Safety analysis

The safety data (adverse events)- both numbers of subjects and events – will be summarised by randomised group and overall using descriptive statistics. No formal statistical tests comparing the randomised groups will be pre-specified.

Software for statistical analysis

The statistical software to be used is either SAS 9.2 for Windows, Cary, NC, USA or SPSS Version 22.

PrEPAID Statistical Analysis Plan (Version 1.0)
 Approval date:

Table 1: Participant characteristics at baseline

	PE+TENS	PE+ Placebo TENS	TENS	Placebo TENS
Age				
Sex (%male)				
Ankle-brachial index				
Diagnosis of PAD				
Date of diagnosis:				
\geq 3months <6months				
\geq 6months<12months				
\geq 12months				
Type of PAD				
Iliac				
Femoral				
Popliteal				
Other				
Diagnosis of IC				
Date of diagnosis:				
\geq 3months <6months				
\geq 6months<12months				
\geq 12months				
Limb affected				
Left				

PrEPAID Statistical Analysis Plan (Version 1.0)

Approval date:

Right				
Both				
Fontaine Classification				
I				
II				
III				
IV				
Past Medical History				
IHD: Y/N				
MI: Y/N				
LVH: Y/N				
Cardiac risk factors				
DM : Y/N				
Family History of IHD/CVA/ BP: Y/N				
Hypercholesterolemia: Y/N				
Hypertension: Y/N				
Alcohol excess:				
Current				
Previous				

PrEPAID Statistical Analysis Plan (Version 1.0)

Approval date:

Never				
Smoking:				
Current				
Previous				
Non-smoker				
Present drug history:				
Statin Y/N				
Antiplatelet Y/N				
Anticoagulant Y/N				
Outcome measures				
Treadmill maximal walking distance				
Treadmill pain free walking distance				
Daily steps				
Pain intensity(VAS)				
McGill pain score				
QoL SF-36 score				
ICQ score				
Geriatric depression questionnaire score				
Pain self-efficacy questionnaire score				
Brief illness perception questionnaire				

Table 2: Feasibility related outcome tables

Participants recruitment					
Total number of participants screened(n)					
Total number of eligible participants (n/%)					
Reasons for non-eligibility					
X (n/%)	Whole study sample	PE+TENS	PE+ Placebo TENS	TENS	Placebo TENS

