Recruitment target/Number recruited.					
Recruitment rate (n/centre/month)					
Outcome completion rate					
Reasons for withdrawal from intervention					
Retention rate (proportion of participants with valid primary outcome data at 3-months follow-up)					
Retention rate (proportion of participants with valid ActivPAL outcome data at 3-months follow-up)					
Reason for withdrawal from follow up					
Timing of withdrawal					
Intervention uptake and Adherence rate					
Attendance to PE					
Summary from phone calls					
TENS log summary					
Objective record of TENS use					
Acceptability of intervention					
Acceptability questionnaire					
Adverse events rate					
List them					
TENS blinding					

PrEPAID Statistical Analysis Plan (Version 1.0)
 Approval date:

Table 3: Changes in groups' outcomes at 6-wweks compared to placebo (usual care alone)

	TENS	PE+TENS	PE
ACD	$x \pm sd$ vs $x \pm sd$; $p=xxx(95\%cl)$		
ICD			
Daily steps			
Upright events			
Walking events			
EBCD			
ICQ			
SF-36			
7-day Average pain intensity			
Pain quality			
IPQ			
GDS-SF			
PSEQ			

*Also compare between PE+TENS and each of TENSs and PE alone (May not present in a table)

PrEPAID Statistical Analysis Plan (Version 1.0)
 Approval date:

Table 4: Changes in groups' outcomes at 3 months compared to placebo (usual care alone)

	TENS	PE+TENS	PE
ACD	$x \pm sd$ vs $x \pm sd$; $p=xxx(95\%cl)$		
ICD			
Daily steps			
Upright events			
Walking events			
EBCD			
ICQ			
SF-36			
7-day Average pain intensity			
Pain quality			
IPQ			
GDS-SF			
PSEQ			

*Also compare between PE+TENS and each of TENSs and PE alone ((May not present in a table)

Table 5: Within group comparisons between baseline and after 6 weeks intervention and 3 months follow up

	TENS	PE+TENS	PE	Usual care alone
ACD Post 6 wks Post 3 months follow up	$x \pm sd$ vs $x \pm sd$; $p = xxx$ (95%cl)			
ICD Post 6 wks Post 3 months follow up				
Daily steps Post 6 wks Post 3 months follow up				
Upright events Post 6 wks Post 3 months follow up				
Walking events Post 6 wks Post 3 months follow up				
EBCD Post 6 wks Post 3 months follow up				
ICQ Post 6 wks Post 3 months follow up				
SF-36 Post 6 wks Post 3 months follow up				
7-day mean pain intensity Post 6 wks Post 3 months follow up				
Pain quality				

PrEPAID Statistical Analysis Plan (Version 1.0)
Approval date:

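### Adverse events are summarised in four arms of 20 and overall, with no pooled active-TENS or placebo-TENS figure, no interval and no stated period

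*SAP*

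**What the plan says.** The safety paragraph in SAP Section 6 and protocol 8.5 carry the same rule. Adverse events, counted as "both numbers of subjects and events", "will be summarised by randomised group and overall using descriptive statistics". The SAP adds: "No formal statistical tests comparing the randomised groups will be pre-specified". SAP Section 3 (Framework) repeats the rule.

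The Table 2 shell has five columns: "Whole study sample", PE+TENS, PE+Placebo TENS, TENS and Placebo TENS. Safety has one row, "Adverse events rate", and beneath it a line for itemising the events. The row shows no period, denominator or interval.

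Follow-up depends on recruitment date. Treatment lasts six weeks for everyone, and "patients recruited within the first eight months will be further followed up for 3 months" (SAP Section 3, Trial design). Protocol 7.1 defines an adverse event broadly, as "Any untoward medical occurrence in a subject to whom a medicinal device has been administered", whether or not the device caused it. Protocol 7.3 says participants will be asked about "any case of itching, skin breakdown, mild electrical burn, other skin allergies, or mild autonomic responses at each study visit". The visit tables in the protocol's Study Schedule and section 4.1 list an adverse event questionnaire at Visit 4 and not at Visit 5.

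**The concern.** Safety is part of the first research question, and monitoring of adverse events is a stated objective. A team planning the definitive trial will want to know how often adverse events occur with the active device during treatment, and how that compares with the placebo device. The TENS factor of the 2x2 design supplies 40 participants for each. The plan presents either 20 at a time, or all 80 with both devices together.

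The overall column does not fill the gap. Active units run at an intensity the participant finds strong but comfortable (protocol 6.1), and placebo units at about 6 mA (protocol 6.2). Several events of special interest, such as mild electrical burn and skin breakdown, could plausibly depend on that setting, so a figure across both devices describes neither.

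The missing period is a separate matter. Efficacy is tabulated at six weeks and at three months in SAP Tables 3 to 5, but safety has no such split. The choice of window is therefore left open until the data are in hand.

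**Working it through.** **1. Group sizes.** Protocol 8.7 uses a difference of 1.0 SD, two-sided 5% and 80% power. The normal approximation gives n = 2 × (1.960 + 0.842)² / 1.0² = 15.7, so 16 per group. (The t distribution gives 16.7, so 17; this has no bearing here.) With 20% attrition, 16 / 0.80 = 20 per arm, and 4 × 20 = 80 in all. The plan's figures are reproduced. Two arms hold active TENS and two hold placebo TENS, so each device has 2 × 20 = 40. Neither document gives a precision figure for safety.

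**2. Precision by group size.** With zero events, the exact (Clopper-Pearson) two-sided 95% upper limit is U = 1 − 0.025^(1/n). The chance of at least one event at true risk p is 1 − (1 − p)^n. The documents give no event risk, so p = 5% is an assumption. The rows for 16 and 32 apply the plan's 20% attrition.

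| Participants | Upper 95% limit, zero events | Chance of at least one event, p = 5% |
|---|---|---|
| 16 (one arm after attrition) | 20.6% | 56% |
| 20 (one arm) | 1 − 0.025^(1/20) = 16.8% | 1 − 0.95^20 = 64% |
| 32 (two arms after attrition) | 10.9% | 81% |
| 40 (two arms) | 1 − 0.025^(1/40) = 8.8% | 1 − 0.95^40 = 87% |

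If 10% of participants have an event, the exact 95% interval is 1.2% to 31.7% for 2/20 and 2.8% to 23.7% for 4/40.

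**3. What the overall column shows.** With equal numbers on each device, its expected value is (active risk + placebo risk) / 2. For illustration, with assumed risks:
- 10% and 2% give 6.0%
- 10% and 5% give 7.5%
- 20% and 5% give 12.5%

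**4. The period, set side by side.**
- *When events are asked about.* Protocol 7.3 says every study visit. The visit tables schedule the questionnaire at Visit 4 only.
- *When Visit 5 falls.* The protocol (Visit 5 heading) counts three months from the end of the intervention: 6 + 13 = about 19 weeks from the start of treatment. SAP Section 3 (Timing of outcome assessments) counts three months from randomisation: about 13 weeks from that date. Visit 3 falls within 3 weeks after randomisation, so on the SAP's reading Visit 5 comes 13 − 3 − 6 = 4 to 13 − 0 − 6 = 7 weeks after treatment ends, before allowing for visit windows. On the protocol's reading it comes about 13 weeks after.
- *Who attends Visit 5.* Only those recruited in the first eight months. Their share of the 80 is not stated.

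The length of observation behind the adverse event row therefore differs between participants, by an amount the two documents do not agree on.

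**The case against.** The strongest reply is that nothing is lost. The PE+TENS and TENS columns hold only participants allocated an active device, and numbers of subjects are reported by arm, so anyone can add two cells to get a count out of 40. The overall column is an extra and hides nothing. With at most 80 participants, the itemised list will show which events occurred in which arm. Much of this stands. A reader might infer that the report will contain no estimate of the risk with active TENS; the documents do not support that. What remains is that the pooled figure and its interval are not planned. SAP Section 4 has a general statement about 95% confidence, but the safety paragraph asks only for descriptive statistics and the Table 2 row shows no interval.

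A second reply concerns the period. A reader might infer that events from six weeks and from the longer follow-up will be combined into one inflated rate. The plan does not say so; it is silent. The one scheduled questionnaire comes at the end of treatment for everyone, so a six-week summary of the events of special interest can be built from planned data. Any size put on such inflation would need an event rate after treatment stops, which the documents do not give. For skin events that cease when TENS stops, it would be about nil. The cut by recruitment date should also be roughly balanced across arms, so it affects the absolute risk more than the contrast between arms.

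A third inference would be that the denominators are wrong because some participants may leave before receiving a device. The documents give no figure for such losses, and the effect is small: if one of 20 left, 2/20 = 10.0% would become 2/19 = 10.5%.

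**Conclusion.** The point holds as a gap in presentation and precision. Adverse events are planned by four arms and overall, without a pooled figure for each device, without an interval and without a period. Pooling each device's two arms roughly halves the upper 95% limit at zero events (16.8% to 8.8%). It also raises the chance of seeing at least one event at a 5% risk from 64% to 87%.

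These figures assume full recruitment of 20 per arm and, for the second pair, the 5% risk chosen for illustration. They also treat the education component as not materially changing the risk of an adverse event with the device, which is why the four arms should stay visible. The weight is modest: this is a feasibility trial of a CE-marked device that the protocol regards as low risk, and safety is descriptive. The change is still worth making, because it is nearly free and gives the definitive trial a figure for each device over a named period.

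**What to change.** In SAP Section 6 (Safety analysis) and Table 2, and in protocol 8.5 to match:

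1. Keep the four arms and add two columns: active TENS (PE+TENS and TENS) and placebo TENS (PE+Placebo TENS and Placebo TENS). Give the number and percentage of participants with an event, with an exact 95% confidence interval, and the number of events. No test is needed.
2. Split the adverse event row in two: events up to Visit 4 for all participants, and events between Visit 4 and Visit 5 for those due that visit. State the denominator of each.
3. Reconcile protocol 7.3 with the visit tables on the visits at which adverse events are queried.
4. Reconcile the protocol and the SAP on whether the three-month visit is counted from the end of the intervention or from randomisation.

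The pooled columns and the up-to-Visit-4 row use data already planned. The later row depends on how item 3 is settled. The cost is some SAP wording and a slightly longer table.
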